Appendix K. 70-Day Follow-Up Call – Sample

Site Name/Number: _____

Subject Number: _____

Please contact subjects who discontinue adalimumab 70 days following study drug discontinuation.

Date of Call: _____

- Lost to Follow-up (Please check this box if subject was not willing to provide any follow-up information or you were unable to speak to the subject following at least three attempts.)
- No Events Reported

List any Adverse Events (AE) and/or Serious Adverse Events (SAE) that occurred since the subject was last seen in clinic for this study. If needed, provide AE/SAE details on the AE worksheet attached. (Please report all SAEs to AbbVie within 24 hours of being made aware of the event.)

_____	_____
_____	_____
_____	_____
_____	_____
_____	_____
_____	_____

If events are listed above, your monitor will review and retrieve the appropriate eCRF pages during their next visit.

Appendix L. Injection Instructions – Sample Vial

Subject Instructions

0.8 mL dose

Protocol M11-290

Tables of Contents

Dosing Schedule

General Information and Supplies

Injection Procedures

Study Drug Dosing Schedule

Subject Number: _____

You will require subcutaneous (SC) injections throughout the study.

The injection for the visits at Baseline, Weeks 1, 2, 4, 8, 12, 18, 26, 34, 42 and 52 will be done during your visit at the doctor's office. After Week 4, on weeks between office visits (i.e., Weeks 6, 9, 10, 11, 13, etc.) study drug will be self-administered at home by you or someone trained to give you the injections.

The study drug should be administered on the same day of the week for each dose.

Starting at Week 8, study drug will be administered once a week by you or someone trained to give you the injections.

The vials in the kits will be numbered 1 and 2. You MUST use the vials in order.

At each visit, site personnel will measure your weight and inform you the volume of study drug that you will be taken (milliliter [ml] or cc). You must use the suggested volume up until your site personnel provide you with the new volume of study drug to be taken.

Please return all used and unused vials, the Sharps container and empty boxes to the clinic on your next visit. Used syringes should be placed in the special Sharps container provided. All unused vials should be returned in the original box.

If an injection is missed or something occurs where the suggested dose cannot be injected, contact your study center immediately for further instructions. Please record any missed doses on your subject diary/dosing log.

Remember to complete your dosing log after each injection and to call the doctor's office if you are having problems administering your study medication.

General Information

- Vials will be labeled "Adalimumab" versus Placebo.
- Store all adalimumab vials in your refrigerator NOT in the freezer. Should the medication accidentally become frozen, call your study doctor's office.
- Study medication should be taken at about the same time of day, on the same day of the week as directed by your study doctor.
- USE A NEW VIAL AND NEW SYRINGE EVERY INJECTION DAY. There may be medication left in the vial. DO NOT RE-USE.
- Save all study medications. ***All vials (used and unused) and empty boxes must be returned to the study center at each visit.*** Used syringes will be disposed of in a Sharps container provided to you.
- Whenever possible, have someone with you for at least 15 to 30 minutes after your injection.
- Call your doctor IMMEDIATELY if you experience any itching, hives, shortness of breath, or any symptom that has you concerned. If you are unable to reach your doctor or if you experience life-threatening symptoms, **call** _____ or proceed to your nearest emergency room.

Injection Procedures (Vials)

1. Setting up for an injection

- Find a clean flat surface.
- Do not use if the seals on the carton are broken or missing. Contact your study doctor's office if the seals are broken.
- Take one kit with the vial(s) of adalimumab from the refrigerator. Do not use a vial that has been frozen or if it has been left in direct sunlight.
- Return any unused vial(s) to the refrigerator.

You will need the following items for each dose:

- study medication

[figure not shown]
- sterile capped syringe(s)
- alcohol prep(s)
- cotton ball or gauze pad(s)

If you do not have all of the items you need to give yourself an injection, call your study physician. Use only the items provided in the box your adalimumab comes in.

- Make sure the liquid in the vial is clear and colorless. Do not use if the liquid is cloudy or discolored or has flakes or particles in it.
- Have a special Sharps (puncture proof) container nearby for disposing of used needles and syringes.

For your protection, it is important that you follow these instructions.

2. Choosing and preparing an injection site

[figure not shown]

- Wash your hands well.
- Choose a site on the front of your thighs or your stomach area (abdomen). If you choose your abdomen, you should avoid the area 2 inches around your belly button (navel).

- Choose a different site each time you give yourself an injection. Each new injection should be given at least 1 inch from a site you used before. Never inject into areas where the skin is tender, bruised, red or hard or where you have scars or stretch marks.
- If you have psoriasis, you should try not to inject directly into any raised, thick, red or scaly skin patches or lesions.
- You may find it helpful to keep notes on the location of your injection sites.
- Wipe the site where adalimumab is to be injected with an alcohol prep (swab), using a circular motion. Do not touch this area again until you are ready to inject.

[figure not shown]
3. How to prepare your adalimumab dose for injection with a vial

- Remove the plastic cap from the vial.
- Wipe the gray stopper with an alcohol swab and discard alcohol swab.

- Place the vial upright on a hard, flat surface.
- Remove the needle cover from the syringe. (The needle is sterile, so be very careful not to touch the needle or allow it to touch any surface.)
- With the vial sitting on a hard, flat surface, insert needle straight down through the center of the gray stopper. If the needle is correctly lined up, you should feel slight resistance and then a "pop" as the needle penetrates the center of the stopper. *(Be careful not to insert the needle at an angle as this may cause the needle to bend. If the needle is not correctly aligned, you will feel constant resistance as it penetrates the stopper and will not feel a "pop.")*
- Push the plunger in, forcing air into the vial.

- With the needle still in place, turn the vial upside down. Keeping the vial at eye level, slowly pull the plunger back to draw the liquid into the syringe. This will cause the bubbles to rise to the top of the syringe. *(As the liquid level in the vial drops, you may have to withdraw the needle partially to keep the tip of the needle in the liquid.)*
- Adjust the volume in the syringe to the quantity advised by your physician.
- With the needle still in the vial, check the syringe for air bubbles. To remove any air bubbles, start by gently tapping the syringe.
- Slowly press the plunger to push any bubbles out of the syringe and into the vial. (If you accidentally push any liquid back into the vial, draw the liquid back into the syringe and check again for air bubbles. It's okay for a small amount of liquid to remain in the vial.)
- Withdraw the needle from the vial, being careful not to touch it to any surface.
- Take the syringe in one hand.
- Hold the syringe upright with the needle facing down.
- Turn the syringe so the needle is facing up and slowly push the plunger in to push the air in the syringe out through the needle. If a small drop of liquid comes out of the needle that is okay.
- Do not shake the syringe.

4. Injecting Adalimumab

- With your other hand, gently squeeze an area of the cleaned area of skin and hold it firmly.
- You will inject into this raised area of skin. Hold the syringe like a pencil at about a 45° angle (see picture) to the skin.

- With a quick, short, "dart-like" motion, push the needle into the skin.
- After the needle is in, let go of the skin. Pull back slightly on the plunger. If blood appears in the syringe it means that you have entered a blood vessel. Do not inject adalimumab. Pull the needle out of the skin and repeat the steps to choose and clean a new injection site. Do not use the same syringe. Dispose of it in your special Sharps container. If no blood appears, slowly push the plunger all the way in until all of the adalimumab is injected.
- When the syringe is empty, remove the needle from the skin keeping it at the same angle it was when it was pushed into the skin.
- After injection, immediately apply a single finger stroke to the Activation-Assist™ lever arm to activate the shielding mechanism.

- Press a cotton ball or gauze pad over the injection site and hold it for 10 seconds. Do not rub the injection site. You may have slight bleeding. This is normal.
- Dispose of the syringe right away into your Sharps container.

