During open-label rescue therapy, subjects who are responders and have been in remission for at least 8 consecutive weeks ($PMS \leq 2$ with no individual subscore > 1) may have their dosage decreased from ew to eow. The investigator should receive prior approval from the Medical Monitor before taking any action with regard to dose de-escalation.

If subjects demonstrate disease flare after dose de-escalation, subjects also have an opportunity to re-escalate their dose back to adalimumab ew dosing. The investigator should receive prior approval from the Medical Monitor before taking any action with regard to dose re-escalation.

For subjects who meet the criteria for dose change, blood samples (for the determination of adalimumab and AAA concentrations, hs-CRP) will be collected just prior to receiving any dose change (blinded therapy, escape to open-label adalimumab, dose de-escalation and dose re-escalation).

No study drug will be administered or injected at the final visit.

Subjects may discontinue adalimumab treatment at any time during study participation. Subjects who end study participation early will have a Termination Visit. All subjects will have a follow-up phone call approximately 70 days after the last administration of study drug to obtain information on any new or ongoing AEs.

Re-screening

Subjects who initially screen fail for the study may be permitted to re-screen following re-consent. All screening procedures with the possible exceptions noted below will be repeated. The subject must meet all inclusion and none of the exclusion criteria as far as they are assessable at the time of re-screening in order to qualify for the study. There is no minimum period of time a subject must wait to re-screen for the study. If the subject had a complete initial screening evaluation including the assessment of a PPD test, (or equivalent), or Interferon-Gamma Release Assay (IGRA; QuantiFERON-TB Gold In-Tube test or T-SPOT TB test), chest x-ray (if applicable), x-ray of the wrist and ECG, these tests will not be required to be repeated for re-screening provided the conditions noted in Section 5.3.1.1 are met and no more than 3 months (90 days) have passed. An endoscopy will not be required to be repeated for re-screening provided that the prior endoscopy confirmed subject's eligibility, the conditions noted in Section 5.3.1.1 are met and no more than 56 days have passed from Baseline.

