2nd Time (at least Maximum dose of 40 mg
 after 4 weeks of *Maximum amount to administer is 0.8 mL*
 re-induction dose) Administered every week

Dose Escalation (MAX DOSE – NOT Weight Based)

Disease Flare Adalimumab 40 mg/0.8 mL
3rd Time (after at Adalimumab 40 mg
 least 4 weeks on *Amount to administer is 0.8 mL*
 open-label standard Administered every week
 dose)

Dose De-Escalation and Dose Re-Escalation During Maintenance Period

Dose De-Escalation	Open-label study drug adalimumab 40 mg/0.8 mL Administered every other week
Dose Re-Escalation	Open-label study drug adalimumab 40 mg/0.8 mL Administered every week

After Amendment 4

During the Open-Label Induction Period

Week	High Induction Dose
0 (Baseline)	Open-label study drug adalimumab 2.4 mg/kg Maximum dose of 160 mg Maximum amount to administer is 3.2 mL
1	Open-label study drug adalimumab 2.4 mg/kg Maximum dose of 160 mg Maximum amount to administer is 3.2 mL
2	Open-label study drug adalimumab 1.2 mg/kg Maximum dose of 80 mg Maximum amount to administer is 1.6 mL
4	Open-label study drug adalimumab 0.6 mg/kg Maximum dose of 40 mg Maximum amount to administer is 0.8 mL
6	Open-label study drug adalimumab 0.6 mg/kg Maximum dose of 40 mg Maximum amount to administer is 0.8 mL

During the Maintenance Period

Week	Standard Maintenance Dose	High Maintenance Dose
8 – 50 i.e., Wks 8, 10, 12, 14, 16, 18 to Wk 50)	Blinded Study Drug adalimumab 0.6 mg/kg Maximum dose of 40 mg Maximum amount to administer is 0.8 mL	Blinded Study Drug adalimumab 0.6 mg/kg Maximum dose of 40 mg Maximum amount to administer is 0.8 mL
9 – 51 i.e., Wks 9, 11, 13, 15, 17, 19... to Wk 51	Matching PBO Maximum amount to administer is 0.8 mL	Blinded Study Drug adalimumab 0.6 mg/kg Maximum dose of 40 mg Maximum amount to administer is 0.8 mL

Disease Flare During Maintenance Period

Week	Standard Maintenance Dose		High Maintenance Dose	
	Re-Induction Dose of 2.4 mg/kg (max 160 mg)	Dose 0.6 mg/kg (max 40 mg)	Re-Induction Dose of 2.4 mg/kg (max 160 mg)	Dose 0.6 mg/kg (max 40 mg)
Disease Flare				

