Re-Induction Dose (1 st time) At or after Week 12	Blinded study drug adalimumab 2.4 mg/kg Maximum dose of 160 mg Maximum amount to administer is 3.2 mL	Blinded study drug adalimumab 0.6 mg/kg Maximum dose of 40 mg Plus Matching Placebo Maximum amount to administer is 3.2 mL	Blinded study drug adalimumab 2.4 mg/kg Maximum dose of 160 mg Maximum amount to administer is 3.2 mL	Blinded study drug adalimumab 0.6 mg/kg Maximum dose of 40 mg Plus Matching Placebo Maximum amount to administer is 3.2 mL
One week after Re-Induction dose	If subject receives Re-Induction dose at site on Even week (i.e., Wk 22, 24, 26, ...), then subject must start with vial 2 at home at the week after Re-Induction dose. Matching PBO Maximum amount to administer is 0.8 mL The following weeks, subject will use vial 1, then vial 2, continue like this until next site visit.		If subject receives Re-Induction dose at site on Even week (i.e., Wk 22, 24, 26, ...), then subject must start with vial 2 at home at the week after Re-Induction dose. Blinded study drug adalimumab 0.6 mg/kg Maximum dose of 40 mg Maximum amount to administer is 0.8 mL The following weeks, subject will use vial 1, then vial 2, continue like this until next site visit.	

Disease Flare During Maintenance Period (Continued)

Week	Standard Maintenance Dose		High Maintenance Dose	
	Re-Induction Dose of 2.4 mg/kg (max 160 mg)	Dose 0.6 mg/kg (max 40 mg)	Re-Induction Dose of 2.4 mg/kg (max 160 mg)	Dose 0.6 mg/kg (max 40 mg)
Disease Flare				
One week after Re-Induction dose (continued)	
If subject receives Re-Induction dose at site on Odd week (i.e., Wk 21, 23, 25, ...), then subject must start with vial 1 at home at the week after Re-Induction dose.
 
Blinded study drug adalimumab 0.6 mg/kg Maximum dose of 40 mg Maximum amount to administer is 0.8 mL
 
The following weeks, subject will use vial 2, then vial 1, continue like this until next site visit.
		
If subject receives Re-Induction dose at site on Odd week (i.e., Wk 21, 23, 25, ...), then subject must start with vial 1 at home at the week after Re-Induction dose.
 
Blinded study drug adalimumab 0.6 mg/kg Maximum dose of 40 mg Maximum amount to administer is 0.8 mL
 
The following weeks, subject will use vial 2, then vial 1, continue like this until next site visit.
	

Escape to Open-Label Drug (Weight Based)

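### Appendix L's unconditional vial order contradicts Appendix G after an even-week flare dose; followed literally, it swaps active and placebo weeks in the every-other-week regimens until the next visit

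*Protocol*

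**What the plan says.** Protocol Appendix L, the sample leaflet for subjects, gives one rule for all circumstances: "The vials in the kits will be numbered 1 and 2. You MUST use the vials in order". Section 5.5.2.1 names this appendix as the source of detailed instructions and training on administration.

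Protocol Appendix G gives a rule specific to the period after a flare dose, and it depends on the week. For an even-week dose, "then subject must start with vial 2 at home at the week after Re-Induction dose". After that first home injection, "The following weeks, subject will use vial 1, then vial 2, continue like this until next site visit". For an odd-week dose, "then subject must start with vial 1 at home at the week after Re-Induction dose". In the standard-dose column, the first vial after an even-week flare dose is matching placebo and the first vial after an odd-week flare dose is adalimumab. The pre-Amendment 4 tables give the same rule to placebo subjects once they have been re-randomized for a flare.

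Section 5.1 has standard-dose subjects return to every-other-week dosing on their original calendar after the flare dose. In Appendix G that calendar puts active drug on even weeks ("i.e., Wks 8, 10, 12, 14, 16, 18 to Wk 50") and placebo on odd weeks, up to Week 51.

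On the last visit, Appendix L says "The injection for the visits at Baseline, Weeks 1, 2, 4, 8, 12, 18, 26, 34, 42 and 52 will be done" at the doctor's office. Section 5.1 says "No study drug will be administered or injected at the final visit".

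**The concern.** After an even-week flare dose a family cannot obey both appendices: one requires vial 1 first, the other vial 2 first. Which vial comes first matters only where the two vials differ. That is the standard-dose arm and the former placebo subjects, who move to the standard dose after a flare. In the high-dose arm both vials are active.

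This is not a rare configuration. Flare re-randomization opens at Week 12, and every scheduled visit at which it can occur (Weeks 12, 18, 26, 34 and 42) is an even week. At stake is unplanned dosing in children. The post-flare safety rates, some pre-dose drug levels and the modified non-responder (mNRI) sensitivity analysis all use data from this period.

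**Working it through.** The plan states no figure here, so the check is a count of weeks.

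**Inputs**
- Standard-dose vial contents: vial 1 active, vial 2 placebo (Appendix G, read from the two post-flare rules above).
- Scheduled visits from Week 12: 12, 18, 26, 34, 42, 52 (Synopsis; Section 5.1).
- Two vials per kit (Section 5.5.2.1). The flare dose uses all four vials of two kits at every weight (Appendix I). Home dosing therefore appears to start from another kit with vial 1 unused. This is an inference.

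**Step 1: does Appendix G agree with its own calendar?** Yes. For every flare week from 12 to 51, its vial rule returns active drug on even weeks and placebo on odd weeks. An even-week flare dose followed by vial 2, 1, 2, … gives placebo in the next (odd) week and active drug in the week after.

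**Step 2: the two orders after an even-week flare dose.** Let the dose be given in week W and the next visit fall in week V, both even. Home injections fall in weeks W+1 to V−1.
- Appendix G order, active on even weeks: (V − W − 2)/2 active home doses.
- Leaflet order, active on odd weeks: (V − W)/2 active home doses.
- Difference: (V − W)/2 − (V − W − 2)/2 = 1.

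| Flare visit to next visit | Active home weeks, Appendix G | Active home weeks, leaflet | Count |
|---|---|---|---|
| 12 to 18 | 14, 16 | 13, 15, 17 | 2 vs 3 |
| 18 to 26 | 20, 22, 24 | 19, 21, 23, 25 | 3 vs 4 |
| 26 to 34 | 28, 30, 32 | 27, 29, 31, 33 | 3 vs 4 |
| 34 to 42 | 36, 38, 40 | 35, 37, 39, 41 | 3 vs 4 |
| 42 to 52 | 44, 46, 48, 50 | 43, 45, 47, 49, 51 | 4 vs 5 |

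An unscheduled even-week flare visit behaves the same way; Week 22 to Week 26 gives 1 vs 2.

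**Step 3: where the difference vanishes.** After an odd-week flare dose both appendices start with vial 1, so the difference is 0. After an even-week flare dose with an unscheduled odd-week next visit, the number of home weeks V − W − 1 is even and splits equally. The weeks are still swapped, but the count difference is 0.

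**Step 4: relative size, flare injection included.** Total active injections are 3 vs 4 (+33%) for Weeks 12–18 and 5 vs 6 (+20%) for Weeks 42–52. For a subject given the 2.4 mg/kg re-induction dose, and ignoring the dose caps:
- Weeks 12–18: 2.4 + 2 × 0.6 = 3.6 mg/kg versus 2.4 + 3 × 0.6 = 4.2 mg/kg (+17%).
- Weeks 42–52: 2.4 + 4 × 0.6 = 4.8 mg/kg versus 2.4 + 5 × 0.6 = 5.4 mg/kg (+12.5%).

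**Step 5: what the analyses see.**
- Protocol Section 5.3.2.1 schedules pre-dose drug samples at Weeks 26, 34 and 52, but not at 18 or 42. In the intervals ending at the sampled weeks, the sample would follow an active dose by one week (25, 33, 51) rather than two (24, 32, 50).
- SAP Section 9.0 defines compliance as injections received over injections planned, so swapped vials can still score 100%.
- SAP Section 6.0 counts re-randomized subjects as non-responders from the first re-randomization in the confirmatory analyses. Under mNRI this happens only from the switch to open-label drug, so only mNRI uses the affected period.

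**The case against.** *Using vials in order may mean no more than alternating 1, 2, 1, 2.* On that reading, the even-week flare dose replaces that week's vial 1, and Appendix G simply continues with vial 2. Appendix G is also the specific rule, while Appendix L is headed a sample and never mentions flares. This is how a careful site might resolve the conflict. It does not remove it: a family opening a kit numbered 1 and 2 reads an unconditional instruction. Section 5.3.1.1 has staff tell families the amount to inject and does not mention vial order.

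*Safeguards exist.* The dosing log records kit and vial number, records are checked at each visit, and a wrong treatment or dose is a reportable deviation (Sections 5.3.1.1 and 7.0). That stands, but these checks find the error after the injection.

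*The effect is small.* This largely stands. A reader might infer that the leaflet adds a dose in every interval or moves children to weekly dosing. The documents do not support that. At the next even-week visit the clinic dose corresponds to vial 1 and the following home dose to vial 2, so the two orders agree again. Home active doses remain every other week throughout; active weeks become adjacent only at the edges of the interval.

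*No confirmatory result is touched, and neither flare arm is favoured.* Both parts stand. The vial rule is identical with and without re-induction, and SAP Section 10.7 only summarizes that comparison.

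*SAP Section 9.1 does not flatly exclude a Week 52 dose.* Correct. It treats such a dose as the first dose of the extension study for subjects who roll over.

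**Conclusion.** The contradiction between Appendix L and Appendix G is in the text and needs correcting. It affects standard-dose subjects and former placebo subjects after a flare dose given in an even week. Following the leaflet literally swaps active and placebo weeks until the next visit. It also gives exactly one more active home dose than Appendix G, in that single interval, when the next visit is an even week.

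This rests on two assumptions: that home dosing starts from a fresh kit, as Appendix I implies, and that site staff do not override the sample leaflet. Nothing in the documents shows that any child was dosed out of sequence, and that should not be inferred.

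High-dose subjects and the confirmatory non-responder analyses are unaffected. Post-flare adverse-event rates, pre-dose levels at Weeks 26, 34 and 52, and the mNRI sensitivity analysis could be affected, to an extent that depends on how many families followed the leaflet.

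The Week 52 entry in Appendix L is a separate, smaller inconsistency. Section 5.1 and Appendix G give no dose at the final visit, and the leaflet does not say that a Week 52 dose would belong to the extension study.

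**What to change.** Reconcile the vial-order instruction across Appendix L, Appendix G and Section 5.1, so that families and sites read one rule for the period after a flare dose. Reconcile the Week 52 entry in Appendix L with Section 5.1, Appendix G and SAP Section 9.1. Then re-issue the subject instructions. Which vial order and which schedule are right is for the sponsor's clinical and drug-supply teams to settle; this review takes no view.

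The cost is a wording change to a subject leaflet, ethics committee review of the revised subject information (Section 9.1), and redistribution to sites. No new procedures, visits or subjects are needed.
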